#### 6.1.1 Individual-level analysis

For the individual-level analysis we will use a mixed-effects regression model using a log link and binomial distribution, with the healthcare centers as random intercepts to estimate a risk ratio. Fixed effects will include randomized arm, and *a priori* covariates for cluster size (“large” vs “non-large” healthcare center), the outcome proportion from 2019 (which was used in the randomization procedure; included as a linear continuous variable). Other covariates will be included if there is a “large” difference between the arms as defined below:

- For binary variables, the difference between the proportion in the arms is greater than 20% (pooling all data and ignoring clusters)
- For continuous variables,  $M_1 > 1.2 \times M_2$ , where  $M_1$  is the mean in the arm with the higher mean, and  $M_2$  is the mean in the arm with the lower mean (pooling all data and ignoring clusters).

#### 6.1.2 Cluster-level analysis

For the cluster-level analysis we use a method described by Hayes & Moulton (Cluster randomised trials, second edition. CRC Press, pp 197-198) to estimate a risk difference. This method allows for the adjustment of individual-level covariates using a two-stage method. In the first stage, an individual-level logistic regression analysis is performed, ignoring the clustering, and excluding the treatment allocation. For each cluster, we then calculate the difference between the number of events (tests, re-tests) expected by the model and the observed number. In the second stage, we compare the cluster summaries from each arm using a standard two-sample t-test. If the difference in expected number of events is systematically different between the arms, we conclude this is due to the effect of the triggering system.

We will adjust, *a priori*, cluster size (“large” vs “non-large”) and outcome proportion in 2019, plus any other baseline characteristics which have a large imbalance between trial arms, as defined above (§6.1.1).

This analysis will be performed using the user-contributed Stata command `clan` (<https://ideas.repec.org/c/boc/bocode/s458844.html>). For full transparency, the trial

statistician [name] was a co-developer of this command. The command is free to use and he does not receive any financial benefit from it.

## **6.2 Sub-group analysis**

Two sub-group analyses are planned: frequency of visits and sex. These will be conducted on the four testing outcomes (A-D) only.

### **6.2.1 Sub-group analysis 1: Repeat visits**

We will categorize each participant according to whether they attended one visit, or more than one visit, during the recruitment phase (12 months for outcomes A and B, 18 months for outcomes C and D). We will include this variable in the individual-level analysis model as an interaction with the treatment variable to assess if the intervention is more effective among patients who attend more frequently.

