### **3.4 Sample size**

The study was adequately powered to detect an absolute improvement in our primary study outcome of 13% with an alpha of 5%. To calculate the power of our trial, we evaluated the processes of care in the 66 primary healthcare centers during 2019 as collected in the SCREAM project. We chose this year prior to the COVID-19 pandemic to have more objective estimations of health use not affected by and policies during the pandemic. During 2019, 662 995 unique individuals visited those primary healthcare centers at least once. Of those, 92 011 were eligible for screening/testing of kidney function: 66% took a creatinine test, and 34% took a creatinine test. Of people with first detected eGFR<60 ml/min/1.73 m^2 or albuminuria, 59% and 28% were retested for creatinine or albuminuria within 3-6 months.

We assumed a recruitment period of 12 months and a total of 33 health center (clusters) per arm with the same number of patients as in 2019. We estimated the intraclass correlation for the outcomes to be 0.1 (as quantified in the UK trial by Major et al, J Am Soc Nephrol. 2019 Jul;30(7):1261-1270.). The table below gives the originally calculated power, and the power we now have, conservatively assuming 32 clusters per arm.

Comparison	Original power (33 clusters per arm)	New power (32 clusters per arm)
A. Primary outcome: Detect an increase of people having a creatinine test from 66% to 79%	86%	85%
B. Detect an increase of people having a albuminuria test from 34% to 48%	84%	83%
C. Detect an increase of people having a re-test of creatinine from 59% to 73%	86%	82%
D. Detect an increase of people having a re-test of albuminuria from 28% to 42%	86%	84%

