#### 4.4 Analysis populations

The unit of observation is the individual patient. Each patient will only be included once in each analysis.

For outcomes A and B, each patient will be included at the time of their first visit during the recruitment phase: we will refer to this as their Index date for that outcome. This will be used as the start time for the 12 months window for testing.

For outcomes C and D, each patient will be included at the time of their results from their creatinine (C) or albuminuria (D) test: we will refer to this as their Index date for that outcome. This will be used as the start time for the 6 months window for re-testing.

There will be an analysis population associated with each of the four outcomes listed above (A-D). Randomisation occurred in September 2023; however, we will allow a four-month run-in period for the new system. Recruitment of individual participants will begin on 1st January 2024. For outcomes A and B, recruitment will close on 31st December 2024, to allow 12 months of follow-up for all patients. For outcomes C and D, recruitment will close on 30th June 2025, to allow six months of follow-up for all patients.

**Modified ITT population A:** All patients who attend a visit at one of the study health centers during 2024 and who remain alive and registered at that center for a further 12 months, and are eligible for annual kidney function screening.

**Modified ITT population B:** Same as Modified ITT population A (above)

**Modified ITT population C:** All patients who receive a test result for creatinine from one of the study health centers between 1st January 2024 and 30th June 2025, who remain alive and registered at that center for a further six months, and have an indication for a re-test.

**Modified ITT population D:** All patients who receive a test result for albuminuria from one of the study health centers between 1st January 2024 and 30th June 2025, who remain alive and registered at that center for a further six months, and have an indication for a re-test.

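### The repeat-visit subgroup is built from visits after randomisation (for A and B, after the index date), so its interaction can depart from 1 without true effect modification

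*SAP*

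**What the plan says.** Section 6.2.1 sets up the first of two planned subgroup analyses: "We will categorize each participant according to whether they attended one visit, or more than one visit, during the recruitment phase". The counting period is "12 months for outcomes A and B, 18 months for outcomes C and D". The variable enters the individual-level model "as an interaction with the treatment variable to assess if the intervention is more effective among patients who attend more frequently".

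Section 4.4 fixes the timing. "Randomisation occurred in September 2023; however, we will allow a four-month run-in period for the new system", and recruitment opens on 1 January 2024. For A and B, "each patient will be included at the time of their first visit during the recruitment phase"; recruitment closes on 31 December 2024, and the 12-month testing window runs from that first visit. For C and D, "each patient will be included at the time of their results from their creatinine (C) or albuminuria (D) test"; recruitment closes on 30 June 2025.

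The SAP attaches no caveat to this subgroup. Its only sensitivity analysis (section 6.5) removes one center and does not bear on this point.

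**The concern.** An arm-by-subgroup interaction shows effect modification only if neither the intervention nor the outcome can change who is in which subgroup. Sex, the other planned subgroup, meets that condition. A count of recruitment-phase visits may not.

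The intervention aims to get eligible people invited and tested (section 2). A test may bring a sampling visit, a visit to discuss the result, or later management visits. If any of these count, a tested patient is more likely to leave the one-visit group than an untested one. The one-visit group then loses tested patients, and loses more of them in the arm with more testing. Equal follow-up behaviour in the two arms does not prevent this once the intervention raises testing.

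At stake is a misleading interaction estimate and interval in one of the two planned subgroup analyses, which cover A–D only.

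**Working it through.** **Timing, from sections 4.4 and 6.2.1**

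| | A and B | C and D |
|---|---|---|
| Randomisation | September 2023 | September 2023 |
| Visits counted | 1 Jan 2024 – 31 Dec 2024 | 1 Jan 2024 – 30 Jun 2025 |
| Index date | first visit in that period | date of the test result |
| Outcome window | 12 months from index | 6 months from index |
| Visit that makes a patient "more than one" | always after index and inside the outcome window | before or after index, always after randomisation |

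**Size for outcome A.** The SAP gives no figure for this subgroup, so there is nothing to reproduce. The illustration uses:

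- From section 3.4: 66% tested in control and 79% in intervention, so RR = 0.79/0.66 = 1.197, applied to every patient. There is no true effect modification.
- Assumed: *a*, the share who would otherwise have one visit (0.2 or 0.5), and *r*, the share of tested one-visit patients who make a further counted visit because of the test.

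With *p1* and *pm* the testing rates in would-be one-visit and multi-visit patients, in each arm:

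- tested share, one visit observed = p1(1 − r) / (1 − p1·r)
- tested share, more than one visit observed = [(1 − a)pm + a·p1·r] / [(1 − a) + a·p1·r]

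Worked case, p1 = pm, a = 0.5, r = 0.3 in both arms:

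- One visit: control 0.66×0.7/(1 − 0.198) = 0.576; intervention 0.79×0.7/(1 − 0.237) = 0.725; RR 1.258.
- More than one: control (0.330 + 0.099)/(0.5 + 0.099) = 0.716; intervention (0.395 + 0.1185)/(0.5 + 0.1185) = 0.830; RR 1.159.
- Ratio of RRs = 1.159/1.258 = 0.921, where the truth is 1.

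All cases with p1 = pm:

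| r control | r intervention | Ratio, a = 0.2 | Ratio, a = 0.5 |
|---|---|---|---|
| 0 | 0 | 1.000 | 1.000 |
| 0.02 | 0.02 | 0.997 | 0.995 |
| 0.05 | 0.05 | 0.992 | 0.987 |
| 0.1 | 0.1 | 0.983 | 0.974 |
| 0.3 | 0.3 | 0.943 | 0.921 |
| 0.1 | 0.3 | 1.057 | 1.070 |
| 0.2 | 0.1 | 0.933 | 0.907 |

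**If would-be one-visit patients are tested less often.** Take control p1 = 0.5 or 0.6, pm = (0.66 − a·p1)/(1 − a), and RR 79/66 in both groups. Over a = 0.2 and 0.5 the ratio is 0.977–0.987 at r = 0.1, 0.929–0.958 at r = 0.3, and 1.078–1.114 for 0.1 in control against 0.3 in intervention. The corner a = 0.5, p1 = 0.5 implies 0.82 × 79/66 = 98% testing in multi-visit intervention patients, which is extreme.

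**A route that does not run through the test.** Suppose half the patients have high need, with control testing 0.80 against 0.52 (average 0.66) and second-visit probability 0.8 against 0.5. Apply RR 1.197 to all. If the intervention raises only the low-need second-visit probability to 0.7, the ratio is 0.918. If it raises only the high-need one to 0.95, the ratio is 1.118. If it changes neither, the ratio is 1.000.

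C and D are not quantified. No false-positive rate is given, because it depends on assumed between-center variation.

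**The case against.** The strongest case against runs as follows.

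- **The inputs are assumed and the distortion may be trivial.** This stands as a limit on size. At r = 2% the ratio is 0.995–0.997. The figures show what can happen and do not predict this trial.
- **Ratios above 1 need an arm difference in visit behaviour.** Correct. With equal *r* and RR above 1, every ratio in the table is at or below 1. The SAP does not say that the trigger changes visits, but it does not rule it out, and an intervention meant to invite people for testing makes it plausible.
- **What counts as a visit may be defined in the protocol.** Fair. The missing definition is not a defect in itself, but it is a reason why the size is unknown. The distortion vanishes if neither testing nor arm affects counted visits. Excluding sampling and result contacts would not guarantee that, as the high-need example shows.
- **The sponsor may want repeated exposure to the trigger, which earlier attendance cannot measure.** This is a legitimate interest. But the stated purpose is "to assess if the intervention is more effective among patients who attend more frequently", and that is an effect-modification question.
- **Little depends on it.** It is one subgroup analysis, and section 4.1 sets no formal significance level. This limits the weight of the point but does not make the interaction interpretable.

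**Conclusion.** The concern holds. The timing follows directly from sections 4.4 and 6.2.1: the subgroup variable arises after randomisation for all four outcomes and, for A and B, inside the outcome window. Read as effect modification, the interaction can be biased in either direction while the true risk ratio is the same in everyone.

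Under the assumed return rates of 10–30%, with equal underlying testing rates, the ratio of risk ratios for A runs from 0.91 to 1.07. It is exactly 1 when visits depend on neither testing nor arm. Its actual size and sign in this trial cannot be known from the SAP. The primary result and the main A–D estimates are not affected, so this is a worthwhile correction and not a threat to the trial's conclusions.

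**What to change.** In section 6.2.1, define attendance frequency from a fixed period before randomisation, for example the 12 months to August 2023, and use that variable in the interaction. The categories must place patients with no earlier visit (for example 0–1 against more than 1). State, or cite, which contacts count as a visit.

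If the recruitment-phase count is kept as a measure of repeated exposure to the trigger, report it by arm as descriptive, with an explicit statement that it supports no causal reading.

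The cost is a few lines of SAP text and one derived variable. Section 3.4 suggests the data are retrievable, since it already counts earlier visitors to these centers: "During 2019, 662 995 unique individuals visited those primary healthcare centers at least once".

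There are two limits. Earlier attendance measures habit and not exposure to the trigger. For C and D the change repairs the subgroup variable, but those populations are still selected by a test result obtained after randomisation.

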### **6.2.2 Sub-group analysis 2: Sex**

We will assess whether the intervention works differently among men and women by including sex in the individual-level analysis model as an interaction with the treatment variable.

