### **3.3 Post-randomization change**

Four days after randomization the study team were informed that two of the 66 centers had been merged into one administrative unit (although still on separate sites). These two centers were Bredäng and Sätra; their new name is “Bredäng Sätra vårdcentral”. Due to the merger we will not be able to retrieve outcome data at a lower level than the merged center. As by chance these two centers had been assigned to the same arm (the intervention) we decided to proceed with the trial under the original randomization. We note here that the two original restrictions still held after the merger of these centers:

1. the population of the new center is 1,455, which means it ranks 24th (of 65) in size
2. the difference between the two arms in terms of 2019 test rates is now 3.4% (< 3.7%)

This SAP is written to reflect that change. We will analyze the study with 65 centers (33 in the standard arm and 32 in the intervention).

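### The subgroup-by-arm interactions are tested with center random intercepts only, so their intervals and p-values are too tight if the subgroup contrast varies between centers

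*SAP*

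**What the plan says.** SAP 6.1.1 defines the individual-level analysis as "a mixed-effects regression model using a log link and binomial distribution", "with the healthcare centers as random intercepts to estimate a risk ratio". The fixed effects are arm, center size class, the 2019 outcome proportion and any covariate with a large imbalance.

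SAP 6.2 plans two subgroup analyses: "These will be conducted on the four testing outcomes (A-D) only". For repeat visits, 6.2.1 states: "We will include this variable in the individual-level analysis model as an interaction with the treatment variable". For sex, 6.2.2 specifies "including sex in the individual-level analysis model as an interaction with the treatment variable". That makes 2 × 4 = 8 interaction tests.

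The SAP names no random slope for the subgroup variable and no cluster-robust variance, and it does not extend the cluster-level method of 6.1.2 to the subgroups. Section 3.5 announces two-sided p-values and confidence intervals for all comparisons. Section 4.1 announces 95% intervals throughout and sets no formal significance level.

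**The concern.** Sex and visit frequency vary within centers, whereas arm varies only between centers. The interaction asks whether the within-center contrast (for example the women-to-men risk ratio) differs on average between 33 standard and 32 intervention centers. Its uncertainty has two parts: sampling error within each center, and real differences in the contrast from center to center. A random intercept absorbs differences in the overall testing rate but not differences in the contrast. The model as written sets that second part to zero.

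With well over a thousand patients per center for outcomes A and B, the within-center sampling error is small, so modest variation in the contrast can matter. At stake is whether a reported difference in effect between men and women, or between single and repeat visitors, carries an honest interval and p-value.

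**Working it through.** The SAP gives no figure for the interactions, so there is none to reproduce. Its power figures in 3.4 concern the main effects and do not bear on this point.

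**Inputs from the SAP**
- Centers: 33 standard and 32 intervention (3.3).
- Patients: "Of those, 92 011 were eligible for screening/testing of kidney function" (3.4), in 66 centers before the merger, so m = 92,011/66 = 1,394 per center.
- Control rates p (3.4): A 66%, B 34%, C 59%, D 28%.
- Clustering: "We estimated the intraclass correlation for the outcomes to be 0.1" (3.4).

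**Assumptions, not in the SAP**
- Half of the patients in each subgroup level, and no true interaction.
- τ, the between-center SD of the subgroup log risk ratio (log RR), from 0 to 0.05. For A, 0.02 is about 0.02 × 66 = 1.3 percentage points and 0.05 about 3.3 points.
- 150 patients per center for C and D.

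**Step 1: equal-size formula**
- Sampling variance of one center's log RR: s² = 4(1−p)/(p·m). For A: 4 × 0.34/(0.66 × 1,394) = 0.00148, so s = 0.0384. For B, s = 0.0746; for C, 0.1361; for D, 0.2619.
- Variance used by the intercept-only model: s²(1/33 + 1/32). For A the SE is 0.0095.
- Actual variance: (s² + τ²)(1/33 + 1/32). For A the SE is 0.0108, 0.0121 and 0.0156 at τ = 0.02, 0.03 and 0.05. At 0.05 the interval should be 0.0156/0.0095 = 1.64 times as wide.
- Real error of a nominal two-sided 5% test: 2[1 − Φ(1.96/√(1 + τ²/s²))].

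**Step 2: simulation**
There were 2,000 runs per setting, with 65 centers whose baseline rates vary at ICC 0.1. Inverse-variance pooling of center log RRs served as a large-cluster stand-in for the intercept-only model. The planned log-binomial mixed model was not fitted. CV is the assumed coefficient of variation of center size.

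| Outcome, method | τ = 0 | 0.02 | 0.03 | 0.05 |
|---|---|---|---|---|
| A, formula | 5.0% | 8.2% | 12.2% | 23.2% |
| A, simulation, equal sizes | 4.9% | 11.9% | 18.8% | 36.9% |
| A, simulation, CV 0.65 | 4.8% | 13.9% | 22.6% | 41.9% |
| B, formula | 5.0% | 5.8% | 6.9% | 10.3% |
| B, simulation, equal sizes | 4.4% | 5.8% | 8.7% | 14.3% |
| B, simulation, CV 0.65 | 4.3% | 6.6% | 10.1% | 17.3% |
| C, formula, 150 per center | 5.0% | 5.2% | 5.6% | 6.6% |
| D, formula, 150 per center | 5.0% | 5.1% | 5.2% | 5.4% |

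The simulated rates exceed the formula because unequal rates and sizes concentrate the pooled weight on fewer centers. A t-test on the center-specific log RRs stayed between 3.8% and 5.8% in all simulated settings.

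**Step 3: is τ above zero plausible?**
At ICC 0.1 and a 66% rate, center rates have an SD of √(0.1 × 0.66 × 0.34) = 0.15. Suppose the subgroup odds ratio is 1.2 in every center.
- In a center with a reference rate of 51%, the other subgroup's rate is 55.5%, so the log RR is 0.085.
- In a center at 81%, it is 83.6%, so the log RR is 0.032.
- Half the difference is about 0.027. A constant odds ratio therefore already gives τ of that order on the log-RR scale.

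Simulating this as the only source of variation, with equal centers and odds ratios of 1.0, 1.1, 1.2 and 1.5, gave rejection rates of 5, 9, 21 and 46% for A and 4, 6, 10 and 25% for B. With the ICC halved to 0.05, A gave 4, 7, 9 and 27%. The t-test on center contrasts stayed at 4% to 6%.

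**The case against.** The strongest counter-argument is that everything depends on τ, which the SAP does not give. If the contrast is the same in every center, the planned test is valid. By the formula, the error for A reaches 10% only at τ of about 0.025, 20% at 0.044 and 50% at 0.105. This stands, and it rules out an unconditional claim. A reader might infer that false subgroup findings are likely under this plan; the documents do not support that. Nor is it right to set τ against the pooled SE of 0.0095 for A. The yardstick is a single center's sampling SD of 0.0384, and τ = 0.02 lies well below it.

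The exact percentages also depend on the assumed spread of center sizes and rates, and they come from a stand-in for the planned model. This stands too, and is why ranges are given.

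Third, the consequence is limited: no formal significance level is set, no decision rests on the subgroup tests, and the shell tables contain no subgroup results. That lowers the weight of the point but does not remove it. Intervals and p-values are announced for all comparisons, and an interval that is too narrow misleads without any threshold.

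What the objection does not answer is Step 3. A subgroup associated with testing through a roughly constant odds ratio, together with the SAP's own ICC, is enough to make the log RR vary. For repeat visits an association is plausible, since more visits give more occasions for a test.

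**Conclusion.** The point holds in conditional form. The interaction models in 6.2.1 and 6.2.2 omit between-center variation of the subgroup contrast, so their intervals and p-values are too tight whenever that variation exists. The effect can be substantial for A and B and is probably slight for C and D if these have few patients per center; their denominators are not stated. The figures rest on an even subgroup split, no true interaction, the 2019 patient numbers and the assumed τ.

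A reader might also infer that the main results are in doubt. They are not: the estimates for outcomes A to D do not depend on the interaction models.

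**What to change.** In SAP 6.2, add to each interaction model a center-level random slope for the subgroup variable, and state that the interaction's interval and p-value come from that model. Name a fallback in case it does not converge: compute each center's own subgroup contrast and compare the 33 standard with the 32 intervention contrasts by t-test. Use risk differences for any outcome in which some center has no events in one subgroup, because the log RR is then undefined.

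This takes a few sentences in the SAP and a few lines of code, and needs no new data. The interaction intervals will be wider if the contrast varies, and the random-slope model is harder to fit. The unweighted t-test targets a center-weighted rather than a patient-weighted interaction, which the SAP should say.
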